4. STUDY DESIGN

4.1. Overall Design

The study will be a randomized, multi-center, open label, placebo study with a 2x2 complete block crossover design. The study will have one visit (although there could be two visits with up to 30 days between the informed consent visit (V0) and the study intervention visit (V1).

Eligible participants with mild to moderate asthma will be randomized to test either the ELLIPTA DPI (containing placebo) followed by BREEZHALER DPI (with placebo capsules), or vice versa in each of the two blocks for the crossover study. Only participants who are naïve to both ELLIPTA and BREEZHALER inhaler will be included.

Participants will demonstrate inhaler use for the first inhaler after reading the relevant sections of the PIL (Attempt 1). If the participant makes any errors, the investigator demonstrates the correct use of the inhaler by conducting a full demonstration as described in the relevant section of the PIL, and the participant will try inhaler use again (Attempt 2). If after the first demonstration by the investigator the participant continues to make errors, the investigator will demonstrate correct inhaler use to the participant up to two additional times (Attempts 3 & 4).

Following each attempted use of the inhaler by the participant, the trained investigator will assess for and document any critical errors (i.e. defined as an error that is most likely to result in no or significantly reduced medication being inhaled) (See [Appendix 3](#)) and non-critical errors made by the participant. This process of error assessment will be used to assess for critical and non-critical errors made by the participant for both inhalers being tested.

At the end of the assessment of the first inhaler, participants will be asked to complete the ease-of-use questionnaire for this device ([Appendix 4](#)) followed by

participant completion of the visual analogue scale (VAS) on their willingness to continue with this inhaler ([Appendix 5](#)).

Participants will be permitted up to a 30-minute break (if required) between completing the assessment of the first inhaler and commencing error assessments for the second inhaler. The second inhaler critical errors assessment follows the same sequence of testing as the first – (Attempts 1 is with no HCP instruction and Attempts 2-4 are with HCP instruction as required).

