8.1.1. Assessment of errors in use of inhalers

- Participants will be randomized to the order of inhaler as detailed in [Table 1](#) and the sequence of questionnaire completion is indicated in the study Schema in Section 1.2. Participants will be provided with the relevant sections of the PIL, explaining the correct use for both inhalers. The critical and overall errors per inhaler and how these have been defined are outlined in [Section 10.3 Appendix 3](#)
- The errors listed will be aligned with the correct use information from the respective PILs, in a checklist for each inhaler which will be provided to the HCPs for scoring errors during the study conduct. The checklists to be completed by the investigator will be provided.

The steps required to assess participant errors in using the inhalers is illustrated in [Figure 1](#) and summarized below:

- Participants will demonstrate inhaler use after reading the use sections of the PIL which is provided to them by the investigator (Attempt 1).
- If the participant makes any errors according to the error checklists in [Appendix 3](#), the investigator demonstrates the correct use of the inhaler, and the participant will try inhaler use again (Attempt 2). If after the first demonstration the participant continues to make errors, the investigator will again demonstrate correct inhaler use to the participant prior to the participant trying again (Attempt 3). If the participant has still not demonstrated correct use, the HCP will again demonstrate correct use for the final time, followed by the final attempt for the participant to demonstrate use of the inhaler (Attempt 4).
- Following each attempted use of the inhaler by the participant, the trained investigator will assess for, and document, any critical errors (i.e., defined as an error that is most likely to result in no or significantly reduced medication being inhaled) and non-critical errors made by the participant.
- This process of error assessment will be used to assess for critical and non-critical errors made by the participant for both inhalers being tested.
- Participants will be permitted up to a 30-minute break between completing the assessment of the first inhaler and commencing error assessments for the second inhaler.

Figure 1 Assessment of errors for each inhaler

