1.1. Objectives, Estimands and Endpoints

1.1.1. Objectives and Endpoints

Table 1 Objectives and endpoints

Primary objective	Endpoint
To compare the proportion of participants who make at least one critical error after reading the section on inhaler use in the patient information leaflets (PILs) for ELLIPTA and BREEZHALER inhalers.	Participants who make at least one critical error after reading the section on inhaler use in the patient information leaflets (PILs).
Secondary Objectives	Endpoints
To compare the proportion of participants who still make at least one critical error after receiving further instruction from the Healthcare Professional (HCP) for ELLIPTA and BREEZHALER inhalers.	Participants who still make at least one critical error after receiving further instruction (up to 3) from the HCP.
To compare the proportion of overall errors made by the participants after reading the PIL, and if necessary, with additional instruction from the HCP for ELLIPTA and BREEZHALER inhalers.	
 Participants who make at least one overall error after reading the PIL(s). Participants who still make at least one overall error after receiving further instruction (up to 3) from the HCP.

To summarize the number of errors (critical and overall) made on each inhaler, with or without further HCP instruction.	Number of errors made after reading the PIL(s), and, if necessary, after receiving further instruction from the HCP.
To compare the proportion of participants that require further instruction from the HCP to demonstrate correct inhaler use for ELLIPTA and BREEZHALER inhalers.	Requiring further instruction from the HCP to demonstrate correct inhaler use.
To compare the Training/Teaching Time required to demonstrate correct inhaler use for ELLIPTA and BREEZHALER inhalers.	
 • The amount of time taken to demonstrate inhaler use without HCP intervention (T1). • The amount of time taken to be given instruction by the HCP (up to 3 times) on use of the inhaler and to demonstrate inhaler use (T2). • The total amount of time taken to demonstrate inhaler use (T1+T2).

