All secondary estimands will use the same population, inhaler comparison and strategy for the intercurrent event as for the primary estimand. Secondary estimands for the proportion of participants who still make at least one critical error after receiving further HCP instruction, the proportion of participants who make at least one overall error after reading the PIL(s) and the proportion of participants who make at least one overall error after receiving further HCP instruction will use the same summary measure as for the primary estimand. Training/teaching time will be summarized using median time for each inhaler.

Each study primary and secondary objective is presented in [Table 2](#) with additional information, including pre-specified estimands with related attributes.

Table 2 Estimands

The following two attributes apply to all estimands listed in the table below:

- Inhaler comparison: ELLIPTA inhaler vs BREEZHALER inhaler
- Population: participants with mild to moderate asthma diagnosis who attempt demonstration of both inhalers (principal stratum strategy).

Objective	Estimand Category	Estimand	Intercurrent Event Strategy	Population Level Summary Measure
		Variable/Endpoint		
Primary Objective: To compare the proportion of participants who make at least one critical error after reading the section on inhaler use in the patient information leaflets (PILs) for ELLIPTA and BREEZHALER inhalers.	Primary	Participants who make at least one critical error after reading the section on inhaler use in the patient information leaflets (PILs).	Not attempting demonstration of the inhaler (ELLIPTA or BREEZHALER).	Odds ratio between ELLIPTA and BREEZHALER.
	Sensitivity		As for primary.	As for primary.
Secondary Objective: To compare the proportion of participants who still make at least one critical error after receiving further instruction (up to 3) from the HCP.	Secondary 1	Participants who still make at least one critical error after receiving further instruction (up to 3) from the HCP.	As for primary.	As for primary.

Objective	Estimand Category	Estimand		
		Variable/ Endpoint	Intercurrent Event Strategy	Population Level Summary Measure
Healthcare Professional (HCP) for ELLIPTA and BREEZHALER inhalers				

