Secondary Objective: To compare the proportion of overall errors made by the participants after reading the PIL, and if necessary, with additional instruction from the HCP for ELLIPTA and BREEZHALER inhalers.	Secondary 2	
a) Participants who make at least one overall error after reading the PIL(s).
 
b) Participants who still make at least one overall error after receiving further instruction (up to 3) from the HCP.
	As for primary.	a) and b) will be summarised as for primary.
Secondary Objective: To summarize the number of errors (critical and overall) made on each inhaler, with or without further HCP instruction.	Secondary 3	Number of errors made after reading the PIL(s), and, if necessary, after receiving further instruction from the HCP.	As for primary.	The number of critical errors and overall errors made for each inhaler (ELLIPTA and BREEZHALER) by instruction (0, 1, 2, 3).

Objective	Estimand Category	Estimand		
		Variable/ Endpoint	Intercurrent Event Strategy	Population Level Summary Measure
Secondary Objective: To compare the proportion of participants that require further instruction from the HCP to demonstrate correct inhaler use for ELLIPTA and BREEZHALER inhalers.	Secondary 4	Requiring further instruction from the HCP to demonstrate correct inhaler use.	As for primary.	The number and percentage of participants who require further instruction from the HCP will be summarized for each inhaler (ELLIPTA and BREEZHALER). A McNemar's test will be used to compare ELLIPTA vs. BREEZHALER.
Secondary Objective: To compare the Training/Teaching Time required to demonstrate correct inhaler use for ELLIPTA and BREEZHALER inhalers.	Secondary 5	a) The amount of time taken to demonstrate inhaler use without HCP intervention (T1). b) The amount of time taken to be given instruction by the HCP (up to 3 times) on use of the inhaler and to demonstrate inhaler use (T2).	As for primary.	a) Median time to demonstrate inhaler use for each inhaler (ELLIPTA and BREEZHALER). b) and c) will be summarised as for a).

Objective	Estimand Category	Estimand		
		Variable/ Endpoint	Intercurrent Event Strategy	Population Level Summary Measure
		c) The total amount of time taken to demonstrate inhaler use (T1+T2).		

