4.3.1.5. Training/teaching time

The population-summary measure for teaching/training time is the median time to demonstrate inhaler use. The median time will be taken from the Kaplan-Meier model. Additionally, the

mean (SD), median, minimum and maximum will also be presented for participants who demonstrate correct inhaler use.

- a) T1: the amount of time taken to correctly demonstrate inhaler use without HCP intervention. Participants who fail to demonstrate the correct use will be censored at the end of T1, having completed demonstration of the first attempt.
- b) T2: the amount of time taken to be given instruction by the HCP (up to 3 times) on use of the inhaler and to demonstrate inhaler use. Participants who demonstrate correct use after reading the PIL (and therefore do not require further instruction) will be considered as demonstrating correct use at T2 and time taken to demonstrate correct use will equal to 0 minutes. Participants who fail to demonstrate the correct use will be censored at the end of T2, after completing the fourth attempt.
- c) The total amount of time taken to demonstrate correct inhaler use until correct demonstration is observed is calculated by: T1+T2. Kaplan-Meier survivor functions of T1+T2 will be obtained for each inhaler group and plotted on the same figure.

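### The Kaplan-Meier T1 median censors failed first attempts that can no longer succeed unaided, so it runs early by an amount the documents do not fix; and the objective to compare training time has no planned comparison.

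*SAP*

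**What the plan says.** SAP 4.3.1.5 a) analyses T1 as the time to correct inhaler use without help from the healthcare professional (HCP), with the median taken from Kaplan-Meier. For failures: "Participants who fail to demonstrate the correct use will be censored at the end of T1". Protocol 9.4.2 has the same rule. As recorded, T1 ends when the first demonstration is finished, whether or not it was correct (Protocol 8.1.2, SAP 4.1.2.1).

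Protocol 4.1 says what follows a failed Attempt 1: "If the participant makes any errors, the investigator demonstrates the correct use of the inhaler". Protocol 6.4 and 8.1.1 agree. Attempts 2 to 4 all come after instruction.

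For T2, SAP 4.3.1.5 b) censors participants who fail all four attempts at the end of the fourth. Item c) forms T1+T2 by addition and plans this display: "Kaplan-Meier survivor functions of T1+T2 will be obtained for each inhaler group and plotted on the same figure". Among participants who succeed, the "mean (SD), median, minimum and maximum will also be presented for participants who demonstrate correct inhaler use".

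The objective in SAP 1.1.1 reads: "To compare the Training/Teaching Time required to demonstrate correct inhaler use for ELLIPTA and BREEZHALER inhalers". The summary measure in SAP 1.1.2 reads: "Training/teaching time will be summarized using median time for each inhaler". Table 2 there (Secondary 5) also names a median for each inhaler and no contrast.

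**The concern.** Censoring a participant says that the event could still happen later and was simply not seen. Here it cannot. Attempt 1 is the only unaided attempt, and its duration and result are both known. Kaplan-Meier nevertheless redistributes each failure's weight to participants who are still demonstrating, as if the failures would have succeeded at the same rate. A T1 median read as the time to correct unaided use is then too early. It can also give a number for an inhaler on which most participants never use the device correctly unaided.

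The second matter is a mismatch inside the SAP. The objective is comparative, but no between-inhaler estimate, confidence interval or test is named for T1, T2 or T1+T2. SAP 4.1.1 and 4.3.1 set the 95% and 5% levels without naming a method for time. The other comparative secondary objectives each have a method: exact conditional logistic regression, McNemar, paired t-test or Prescott (SAP 4.3.1.2 to 4.3.1.4 and 4.3.1.6 to 4.3.1.8). A difference in training time would be judged by eye, without using the pairing or adjusting for period.

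**Working it through.** **The plan's own figure.** The documents give no planning figure for training time. The primary-endpoint sample size reproduces and is not in question: per sequence (1.960 + 1.282)² × 2.785² / (ln 0.3)² = 56.2, rounded up to 57, and 2 × 57 = 114.

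**Direction.** At each moment, both curves use the same hazard of correct completion among participants still demonstrating. The cumulative incidence multiplies that hazard by the share with neither success nor failure so far. Kaplan-Meier multiplies it by its own survival, which counts only successes as losses and so is never smaller. Hence 1 − KM(t) is at least the cumulative incidence at every t, and the Kaplan-Meier median is never later than the time by which half succeed. No distribution is assumed for this step.

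**Inputs for size.**
- Unaided success, p. SAP 5 gives the expert panel's planning rates: 6% with a critical error on ELLIPTA only and 20% on BREEZHALER only. If these are right, unaided success is at most 100 − 6 = 94% and 100 − 20 = 80%. Participants with a critical error on both inhalers, or with non-critical errors only, lower it further; neither share is given. The 60% and 40% rates below are assumptions.
- Correct-attempt time, F: lognormal, median 60 s, log-SD 0.4 (assumed).
- Failed-attempt time, G(t) = F(t/k), with k = 0.5 to 2 (assumed, because the documents are silent).

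**Formulas.**
- Time by which half succeed unaided: p·F(t) = 0.5, with no solution if p is below 0.5.
- Kaplan-Meier median: ∫₀ᵗ p·f(u) / [p(1 − F(u)) + (1 − p)(1 − G(u))] du = ln 2. For k = 1 this reduces to 1 − F(t) = 0.5^(1/p).

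**Example, p = 0.80 and k = 1.** 0.5^(1/0.80) = 0.420, so F = 0.580, z = 0.201 and t = 60·exp(0.4 × 0.201) = 65.0 s. Half succeed when F = 0.5/0.80 = 0.625, so z = 0.319 and t = 60·exp(0.4 × 0.319) = 68.2 s. The gap is 3.1 s before rounding.

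| Unaided success | Half succeed by | KM median, k = 0.5 | k = 1 | k = 1.5 | k = 2 |
|---|---|---|---|---|---|
| 94% | 62.0 s | 60.3 | 61.3 | 61.8 | 61.9 |
| 80% | 68.2 s | 61.1 | 65.0 | 67.2 | 67.9 |
| 60% | 88.4 s | 62.6 | 72.8 | 80.9 | 85.3 |
| 40% | never | 65.1 | 87.0 | 125.2 | not reached |

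The gaps across k = 0.5, 1, 1.5 and 2 are:
- 94% success: 1.7, 0.6, 0.2 and 0.04 s
- 80% success: 7.1, 3.1, 1.0 and 0.3 s
- 60% success: 25.7, 15.6, 7.5 and 3.1 s

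At 40% success and k = 1, the share who have succeeded by the reported median of 87 s is 0.40 × (1 − 0.5^(1/0.40)) = 0.40 × 0.823 = 32.9%, not 50%. The median among successes is 60 s in every row.

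**The case against.** The strongest reply is that a reader of the full report would not be misled. SAP 4.3.1.4 gives the number and percentage needing instruction on each inhaler, with a McNemar test. SAP 4.3.1.3 models any error at Attempt 1 in all participants who attempt both inhalers. The success-only summaries are unaffected by the censoring. An inhaler on which most people fail unaided would be visible. In addition, at the only rates tied to the documents, the gap with equal durations is about 1 s and 3 s, and both measures order the inhalers alike (61 against 65 s; 62 against 68 s). This stands and limits the harm. It does not repair the Kaplan-Meier median, which is the declared summary measure.

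On the comparison, both documents consistently specify a median per inhaler, so description may well be what was meant. In that case the objective's wording is what needs to change.

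A reader might infer more than the documents support:
- *That the distortion is large or favours one inhaler.* The any-error rates and the length of failed attempts are not given, and the gap can be near zero.
- *That a poorly handled inhaler will always show a spurious median.* At 40% success with failed attempts twice as long, Kaplan-Meier does not reach its median either.
- *That four-attempt failures have no rule for T1+T2.* Item c) states none, but censoring follows naturally from item b).
- *That a particular test is required.* Nothing in the plan commits to one.

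**Conclusion.** The T1 rule is wrong as written. The design allows one unaided attempt, so a failed Attempt 1 is a competing outcome; censoring it pulls the T1 median early and can yield a finite median where none exists. The direction needs no distributional assumption.

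The size rests entirely on the assumed lognormal times, failure rates and failed-attempt lengths. It runs from a negligible 0.04 s at 94% unaided success to 25.7 s at 60%, and at 40% the reported median may have no counterpart at all.

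The mismatch between a comparative objective and descriptive outputs is also real, but it can be settled by wording alone. Severity is minor: one secondary endpoint is involved, and the primary analysis and N=114 do not change.

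**What to change.** Before database lock, revise SAP 4.3.1.5 and record the departures from Protocol 9.4.2 in SAP 4.7.

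1. **T1 (main change).** Report the cumulative proportion demonstrating correct unaided use, with failed Attempt 1 kept in the denominator as a competing event. Give the median as *not reached* if fewer than half succeed, and keep the success-only summaries beside it. Treat four-attempt failures the same way for T2 and T1+T2, and write that rule into item c).
2. **Objective.** Choose one:
   - Reword it as *to summarize*, as SAP 1.1.1 already does for the number of errors and the ease-of-use categories, and draw no comparative conclusion on time.
   - At the sponsor's choice, add one paired, period-adjusted between-inhaler estimate for T1+T2 with a 95% confidence interval. State that it is not adjusted for multiplicity (SAP 2.1) and that N=114 was not sized for it.

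The cost is SAP wording and minor programming on data already collected. Item 1 applies whichever option is taken under item 2.

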4.3.1.6. Ease-of-use questionnaire (easy vs. difficult)

The ease-of-use rating from the ease-of-use questionnaire will be rated by participants as: ^{CCI}
 ^{CCI}
 ^{CCI} These ratings will be grouped into easy ^{CCI}
 ^{CCI} or difficult ^{CCI} and a McNemar's test will be performed to test whether the ease-of-use was easy or difficult. The population-summary measure is the number and percentage of participants who rate the inhaler easy to use.

The population-measure summary defined above for ease-of-use will be the same for the following variables as indicated by the ease-of-use questionnaire rated by participants:

- a) Telling how many doses are left in inhaler.
- b) Learning how to use the inhaler.
- c) Handling the inhaler.
- d) Preparing the inhaler.
- e) Holding the inhaler while using it.

4.3.1.7. Willingness to continue with the inhaler

Willingness to continue with the inhaler will be measured on a VAS scale between 0 ^{CCI}
 ^{CCI} to 100 ^{CCI} The difference in means between the ELLIPTA and BREEZHALER inhaler will be presented with 95% CIs and a comparison made between the inhalers (ELLIPTA vs. BREEZHALER) using a paired t-test. The mean, standard deviation, minimum and maximum will also be presented for each inhaler. Histograms and QQ plots will be generated to assess the normality assumption.

